9.2.5. Serious Adverse Events

Serious Adverse Event (SAE): An adverse event or suspected adverse reaction is considered “serious” if, in the view of either the site principal investigator or sponsor, it results in any of the following outcomes:

- Death,
- a life-threatening adverse event*,
- inpatient hospitalization or prolongation of existing hospitalization,
- a persistent or significant incapacity or substantial disruption of the ability to conduct normal life functions, or
- a congenital anomaly/birth defect[¥].
- Important medical events that may not result in death, be life-threatening, or require hospitalizations may be considered serious when, based upon appropriate medical judgment they may jeopardize the patient or subject and may require medical or surgical intervention to prevent one of the outcomes listed in this definition. Examples of such medical events include allergic bronchospasm requiring intensive treatment in an emergency room or at home, blood dyscrasias or convulsions that do not result in inpatient hospitalization, or the development of drug dependency or drug abuse.

*Life-threatening adverse event. An adverse event is considered “life-threatening” if, in the view of either the site principal investigator or sponsor, its occurrence places the patient or subject at immediate risk of death. It does not include an adverse event that, had it occurred in a more severe form, might have caused death.

[†]Congenital anomalies will be reported as described under [Section 9.1](#).

SAEs will be:

- Assessed for severity and relationship to study product and alternate etiology (if not related to study product) by a licensed study physician listed on the Form FDA 1572 as the site principal investigator or sub-investigator. FWs will be trained on the assessment of local and systemic reactogenicity. If the subject reports an AE that is either not included among the solicited AEs or is a grade 3 solicited AE, then the FW will contact a study clinician. The study clinician will either visit the participant at home or the participant will be referred to the study health center based on the FW’s assessment.
- Recorded on the appropriate SAE data collection form and eCRF.
- Followed through resolution by a licensed study physician listed on the Form FDA 1572 as the site principal investigator or sub-investigator.
- Reviewed and evaluated by an Independent Safety Monitor (ISM) (as deemed necessary per [Section 9.6.1](#)), the DSMB (periodic review unless related), DMID, and the IRB, as required by local reporting guidelines.

9.2.6. Procedures to be Followed in the Event of Abnormal Laboratory Test Values or Abnormal Clinical Findings

The site principal investigator or appropriate sub-investigator is responsible for recording all AE/SAEs that are observed or reported during this trial, as described in this protocol, regardless of the relationship to study product. AE/SAEs, or abnormal clinical findings will be collected, assessed, documented, reported, and followed appropriately.

9.3. Reporting Procedures

Solicited injection site and systemic reactogenicity events for pregnant women will be documented and reported from the time of each study vaccination through 7 days after the study vaccination.

Unsolicited non-serious AEs for pregnant women will be documented and reported from the time of study vaccination through approximately 30 days after the study vaccination (Day 31 or delivery, whichever occurs first, for pregnant women).

SAEs among pregnant women will be documented and reported from the time of study vaccination through 6 months postpartum.

For infants, there are no solicited events. AEs and SAEs will be recorded from birth until the 180 days of life for the infant visit. Events that are not medically attended, or that are a part of routine infant health maintenance, will not be reported.

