3.2. Study Outcome Measures

3.2.1. Primary

Safety and Tolerability:

- Safety in pregnant women: Frequency and severity of study vaccine-related serious adverse events (SAEs), and all SAEs in pregnant women from study vaccination through 6 months postpartum, description and comparison between those receiving BOOSTRIX and Td.
- Safety in pregnant women and fetuses/infants: Frequency and severity of adverse events specific to pregnancy, in pregnant women and their infants (as delineated in [Section 9.2.4](#)), description and comparison between those receiving BOOSTRIX and Td.
- Tolerability in pregnant women: Frequency and severity of solicited injection site and systemic reactogenicity events from study vaccination until 7 days following vaccination (Day 8).
- Tolerability in pregnant women: Frequency and severity of all unsolicited non-serious AEs from day of study vaccination to Day 31, description and comparison between those receiving BOOSTRIX and Td.

- Safety in the infants: Frequency and severity of study vaccine-related serious adverse events, and all SAEs in infants from birth through 6 months of age, description and comparison between infants born to women vaccinated with BOOSTRIX and Td.

Immunogenicity:

- Infant humoral immunity: Geometric Mean Concentration (GMC) of serum IgG antibodies to PT as measured by Enzyme-Linked Immunosorbent Assay (ELISA) at birth between infants born to women vaccinated with BOOSTRIX and Td.

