- The newborn infant will be enrolled into the study at the time of birth. A targeted physical examination may be performed by a study clinician licensed to make medical diagnoses and listed on the Form FDA 1572 as the site principal investigator or sub-investigator, if indicated based on review of interim medical history. A physical exam performed by the infant's doctor may also provide information, if required, for documentation.
- Axillary temperature, heart rate, respiratory rate, head circumference, length, and weight will be collected from the medical chart of the infant. If not performed as part of routine care, these measurements, except weight may be taken by qualified members of the research team within 7 days of life. Weights will only be recorded when obtained at birth.
- For infants, study personnel will solicit and record on the appropriate data collection form infant AEs, SAEs, and concomitant medications/vaccinations until the day of life 180

visit. Only medically attended AEs will be recorded. Events associated with routine newborn care and health maintenance visits will not be recorded.

- To collect cord blood and to perform physical examination of the mother and newborn at delivery, an on-call team comprised of a study physician and nurse will be posted at the recruitment site close to the delivery room. This team will collaborate with the local on-call team. The team will refer to the study ID or consent form to confirm the identification of the participant.

7.4.2.2.2. 6 Weeks Postpartum Safety Follow-up Visit, Birth + Day 42 (± 5 d): Clinic Visit, Postpartum Women and Infants (Visit 06 or V06)

- Obtain interim medical history of mother and infant, including an assessment for new medical conditions by interview of subjects and note any changes since the previous clinic visit. Study personnel will solicit and record all new congenital anomalies and SAEs on the appropriate data collection form.
- Study personnel will record infant concomitant medications on the appropriate data collection form.
- A targeted physical examination may be performed by a study clinician licensed to make medical diagnoses and listed on the Form FDA 1572 as the site principal investigator or sub-investigator, if indicated based on review of interim medical history. A targeted physical exam may be performed on the mother, infant, or both.
- 5 mL of infant venous blood will be collected for serology and cytokine assessments.

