9. ASSESSMENT OF SAFETY

9.1. Specification of Safety Parameters

Safety will be assessed by the frequency and severity of the following:

- 1) Study vaccine-related Serious Adverse Events occurring from the time of the study vaccination through the visit 6 months postpartum (180 days of life for the infant visit) for pregnant subjects and infants. All SAEs during this timeframe will be assessed and documented.
- 2) Adverse Events related to pregnancy and the infant as delineated below in [Section 9.2.4](#). For the pregnant woman/mother: pregnancy loss, vaginal bleeding (antepartum or postpartum), post-abortal endometritis/salpingitis, preterm rupture of membranes, preterm contractions/labor/delivery, poor fetal growth, hypertension/pre-eclampsia/eclampsia, chorioamnionitis, postpartum endometritis, gestational diabetes mellitus. For the infant: preterm birth, low birth weight, neonatal complications, and congenital anomalies.
- 3) Solicited Adverse Events – reactogenicity events occurring from the time of study vaccination through 7 days after study vaccination (Day 8) or until resolution.
 - a. Injection site reactions including ecchymosis (bruising), erythema (redness), induration (hardness)/edema(swelling), pain, and tenderness.
 - b. Systemic reactions including fever (days 4 and 8 only during home visits), feverishness (chills/shivering/sweating), fatigue (tiredness), malaise (general unwell feeling), myalgia (body aches/muscular pain exclusive of the injection site), arthralgia (joint pain exclusive of the injection site), headache, nausea, and allergic reaction (pruritus/urticaria).
- 4) Unsolicited Non-Serious Adverse Events – all non-serious unsolicited adverse events will be assessed and documented, and all study vaccine-related non-serious adverse events occurring from the time of study vaccination through approximately 30 days after study vaccination (the Day 31 visit). For pregnant women who deliver before Day 31, unsolicited adverse events will be recorded until delivery.
- 5) Major Congenital Anomalies

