9.3.1. Serious Adverse Events

SAEs will be followed until resolution even if this extends beyond the study-reporting period. Resolution of an AE is defined as the return to pretreatment status or stabilization of the condition with the expectation that it will remain chronic.

Any AE that meets a protocol-defined serious criterion must be submitted immediately (within 24 hours of site awareness) on an SAE form to the DMID Pharmacovigilance Group, at the following address:

DMID Pharmacovigilance Group
Clinical Research Operations and Management Support (CROMS)
[name] [name] 650
[name], USA
SAE Hot Line: [name] (US) or [name] (outside US)
SAE [contact] (US) or [name] (outside US)
SAE Email Address: [contact]

In addition to the SAE form, select SAE data fields must also be entered into the DCC's Advantage eClinical. Please see the protocol-specific MOP for details regarding this procedure. Other supporting documentation of the event may be requested by the DMID Pharmacovigilance Group and should be provided as soon as possible.

The site will send a copy of the SAE report(s) to the ISM (as deemed necessary per [Section 9.6.1](#)) when they are provided to the DMID Pharmacovigilance Group. The DMID Medical Monitor and DMID Clinical Project Manager will be notified of the SAE by the DMID Pharmacovigilance Group. The DMID Medical Monitor will review and assess the SAE for regulatory reporting and potential impact on study subject safety and protocol conduct.

At any time after completion of the study, if the site principal investigator or appropriate sub-investigator becomes aware of an SAE that is suspected to be related to study product, the site principal investigator or appropriate sub-investigator will report the event to the DMID Pharmacovigilance Group.

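### Protocol 9.3 bars reporting of infant events that are not medically attended, with no exemption for SAEs, contradicting 9.1, 9.2.6, 9.3.1 and the primary endpoint of all infant SAEs

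*Protocol*

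**What the plan says.** Four places restrict what is captured for infants.

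- Protocol 9.3 sets the period, "AEs and SAEs will be recorded from birth until the 180 days of life for the infant visit", and then the filter: "Events that are not medically attended, or that are a part of routine infant health maintenance, will not be reported".
- Protocol 7.4.2.2.1 (labor and delivery visit) covers infant AEs and SAEs up to the day-180 visit and adds: "Only medically attended AEs will be recorded".
- The + footnote in Appendix A repeats that last sentence and is attached to one row covering both infant AEs and infant SAEs.
- SAP Table 2 has the same row and the same footnote.

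Other text sets no such condition for serious events.

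- The primary safety endpoint in section 3.2.1 of both documents includes "all SAEs in infants from birth through 6 months of age".
- Protocol 9.1 defines the SAE parameter "through the visit 6 months postpartum (180 days of life for the infant visit) for pregnant subjects and infants" and continues: "All SAEs during this timeframe will be assessed and documented". SAP 4.5.1 says the same.
- Protocol 9.3.1 states: "Any AE that meets a protocol-defined serious criterion must be submitted immediately (within 24 hours of site awareness) on an SAE form".
- Protocol 9.2.6 makes the investigator responsible for recording every AE and SAE that is observed or reported.

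**The concern.** A filter on medical attendance is sensible for minor infant complaints, which would otherwise swamp the record. It does not fit serious events, where the worst outcome may be the one no clinician saw. A hospitalization is attended by its nature, so the filter bites mainly on a death, or another grave event, that happens without care.

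The visit schedule leaves room for this. By nominal days, a pair on the 10-week schedule has no planned contact for 180 − 70 = 110 days, and a pair on the 18-week schedule has none for 130 − 42 = 88 days.

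Two things are at stake: the numerator of a primary safety endpoint (SAP Tables 46 and 61), and the expedited route by which an infant SAE reaches the sponsor's safety group.

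**Working it through.** No figure in the plan needs reproducing. The check sets the passages side by side and applies them to one case.

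**1. Does the 9.3 sentence reach SAEs?** Read literally, yes. Its subject is events in general, and the sentence just before it names AEs and SAEs together. For the women, the same section gives non-serious AEs one sentence and SAEs another, and the SAE sentence has no filter. Only the infant text merges the two and then filters them.

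**2. Do the other three places reach SAEs?** Less clearly. Each restricts AEs, and in 7.4.2.2.1 the sentence before lists AEs and SAEs as separate items, so the more natural reading leaves SAEs alone. Three facts keep it unclear: an SAE is itself a kind of AE, the two footnotes sit on a combined row, and neither document defines medical attendance.

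**3. Does seriousness depend on attendance?** No. Under 9.2.5 an event is serious if "it results in any of the following outcomes", and death heads the list without any condition about care.

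**4. Test case.** An infant dies at home between scheduled visits, and the mother tells staff at the next contact.

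| Text | What it directs |
|---|---|
| 9.3, infant rule | Not reported |
| 7.4.2.2.1, Appendix A and SAP Table 2 footnotes | Unclear |
| 9.1 and SAP 4.5.1 | Assessed and documented |
| 9.2.6 | Recorded, but as the protocol describes, which leads back to 9.3 |
| 9.3.1 | SAE form within 24 hours of awareness |
| 7.4.2.2.2, 7.4.2.2.3 and 7.5 (visits V06 to V08) | New SAEs solicited and recorded |

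The first row cannot stand with the last four, and no sentence ranks them.

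**5. Effect on the analysis.** SAP 9.3 uses the full size of the analysed population as the denominator for event incidence. An infant whose only SAE was left out therefore counts as free of SAEs. Let p₁ and p₀ be the true proportions of infants with an SAE under BOOSTRIX and Td, and let f be the share of those infants with at least one SAE recorded. If f is the same in both arms (an assumption), the tabulated difference is f·p₁ − f·p₀ = f(p₁ − p₀). Both proportions and their difference then shrink by the factor f.

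**6. Size.** The under-count lies between zero, if sites follow 9.3.1, and every unattended infant SAE, if they follow 9.3 literally. The documents give no infant death or SAE rate and no share unattended, so f cannot be estimated.

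**The case against.** The strongest reply is that the protocol read as a whole already captures these events. Section 9.3.1 comes directly after the disputed sentence and has no exception for infants or for unattended events. It routes SAE forms to the sponsor's pharmacovigilance group and, where deemed necessary, to the ISM; 9.6.2 has the DSMB review SAEs regularly. Visits V06 to V08 solicit new SAEs without any attendance condition. After a missed safety assessment, 5.3.4 already calls for three documented attempts to locate the subject or at least learn her health status.

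Much of this stands. A reader of 9.3 alone might infer that an infant death at home goes unreported under the protocol as written and never reaches pharmacovigilance, the ISM or the DSMB. The documents do not support that: once the site knows of the death, 9.3.1 requires the form. It is also fair that three of the four filters name only AEs.

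What the reply does not do is remove the conflict. Section 9.3 is the specific rule for infants, and a site may let it limit the general duties. Nothing says that it may not, and a site that did so could believe itself compliant.

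**Conclusion.** The text is wrong as written. It is an internal contradiction about unattended infant SAEs, and it touches a primary safety endpoint and the expedited-reporting duty. It does not show that such events will be lost, only that a site following 9.3 literally could omit them.

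A reader might go further and infer a particular number of missed deaths, or a distorted comparison between arms. Neither follows. Any count would rest wholly on mortality and care-seeking figures from outside the documents. The trial is double-blind, and nothing in the plan suggests that omission would differ by arm. The finding rests on wording alone and needs no assumption about rates.

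**What to change.** Reconcile the passages by confining the filter to non-serious events in Protocol 9.3, Protocol 7.4.2.2.1, the + footnote in Appendix A and the matching footnote in SAP Table 2. For example:

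*Non-serious infant AEs are recorded only if medically attended; all infant SAEs, including deaths, are recorded and reported whether or not medically attended.*

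The exclusion of routine health-maintenance events in 9.3 should likewise be tied to non-serious events, and a one-line definition of medical attendance would help sites apply the rule. No extra questions are needed at V06 to V08 or at tracing contacts, since the visit procedures and 5.3.4 already cover them.

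The cost is a wording change in four places, with no new visit or sample. The drawback is that cause and relatedness may be less certain for events no clinician saw.

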9.3.1. Serious Adverse Events

SAEs will be followed until resolution even if this extends beyond the study-reporting period. Resolution of an AE is defined as the return to pretreatment status or stabilization of the condition with the expectation that it will remain chronic.

Any AE that meets a protocol-defined serious criterion must be submitted immediately (within 24 hours of site awareness) on an SAE form to the DMID Pharmacovigilance Group, at the following address:

DMID Pharmacovigilance Group
Clinical Research Operations and Management Support (CROMS)
[name] [name] 650
[name], USA
SAE Hot Line: [name] (US) or [name] (outside US)
SAE [contact] (US) or [name] (outside US)
SAE Email Address: [contact]

In addition to the SAE form, select SAE data fields must also be entered into the DCC's Advantage eClinical. Please see the protocol-specific MOP for details regarding this procedure. Other supporting documentation of the event may be requested by the DMID Pharmacovigilance Group and should be provided as soon as possible.

The site will send a copy of the SAE report(s) to the ISM (as deemed necessary per [Section 9.6.1](#)) when they are provided to the DMID Pharmacovigilance Group. The DMID Medical Monitor and DMID Clinical Project Manager will be notified of the SAE by the DMID Pharmacovigilance Group. The DMID Medical Monitor will review and assess the SAE for regulatory reporting and potential impact on study subject safety and protocol conduct.

At any time after completion of the study, if the site principal investigator or appropriate sub-investigator becomes aware of an SAE that is suspected to be related to study product, the site principal investigator or appropriate sub-investigator will report the event to the DMID Pharmacovigilance Group.

9.3.2. Regulatory Reporting for Studies Conducted Under DMID-Sponsored IND

Following notification from the investigator, DMID, the Investigational New Drug (IND) sponsor, will report any suspected adverse reaction that is both serious and unexpected. DMID will report an adverse event as a suspected adverse reaction only if there is evidence to suggest a

causal relationship between the drug and the adverse event. DMID will notify FDA and all participating investigators (i.e., all investigators to whom the sponsor is providing drug under its IND(s) or under any principal investigator's IND(s)) in an IND safety report of potential serious risks from clinical trials or any other source, as soon as possible, but in no case later than 15 calendar days after the sponsor determines that the information qualifies for reporting as specified in 21 CFR Part 312.32. DMID will also notify FDA of any unexpected fatal or life-threatening suspected adverse reaction as soon as possible, but in no case later than 7 calendar days after the sponsor's initial receipt of the information. Relevant follow up information to an IND safety report will be submitted as soon as the information is available. Upon request from FDA, DMID will submit to FDA any additional data or information that the agency deems necessary, as soon as possible, but in no case later than 15 calendar days after receiving the request.

All serious events designated as "not related" to study product(s), will be reported to the FDA at least annually in a summary format.

9.4. Type and Duration of Follow-up of Subjects after Adverse Events

Non-serious AEs will be collected, assessed, and followed through resolution from the time of study vaccination through approximately 30 days after study vaccination. For pregnant women, this period extends from vaccination until Day 31 or delivery, whichever occurs earlier. All unresolved non-serious AEs will be followed through resolution even if this extends beyond the study-reporting period.

SAEs and new-onset chronic medical conditions will be collected, assessed, and followed from the time of study vaccination through resolution even if this extends beyond the study-reporting period. The reporting period extends from vaccination until 6 months postpartum (180 days of life for the infant visit) for pregnant women.

Resolution of an AE/SAE is defined as the return to pretreatment status or stabilization of the condition with the expectation that it will remain chronic.

Follow-up procedures, evaluations, and outcomes will be recorded on the appropriate data collection form.

9.5. Halting Rules

For pregnant women, further enrollment and study vaccinations will be halted for DSMB review/recommendation if any of the following are reported:

- Any subject experiences ulceration, abscess, or necrosis at the injection site related to study product administration.
- Any subject experiences laryngospasm, bronchospasm, or anaphylaxis within 1 day after administration of study product that is considered related to study product.

- Two or more subjects experience generalized urticaria within 3 days after administration of study product that is considered related to study product.
- Any subject experiences a study vaccine-related SAE from the time of study vaccination through subject's last study visit.
- Any subject experiences acute weakness of limbs and/or cranial nerve innervated muscles (description of potential signal of GBS) after administration of study vaccine.

For pregnant women, this study will also be halted for DSMB review/recommendation if, within 7 days after administration of the study vaccination, any of the following occurs:

- 5% or more of subjects (with a minimum of 5 subjects) who received study vaccine experience the same severe (Grade 3) study vaccine-related injection site reaction.
- 5% or more of subjects (with a minimum of 5 subjects) who received study vaccine experience the same severe (Grade 3) study vaccine-related subjective systemic reaction with the exception of allergic reaction, for which the severity (grade) is corroborated by study personnel.
- 5% or more of subjects (with a minimum of 5 subjects) who received study vaccine experience the same severe (Grade 3) study vaccine-related quantitative systemic reaction.
- 5% or more of subjects (with a minimum of 5 subjects) who received study vaccine experience the same severe (Grade 3) pregnancy-related AEs, as found in [Section 9.2.4](#), that are deemed study-vaccine related.

Grading scales for solicited local (injection site) and systemic (subjective and quantitative) reactions are included in [Section 9.2.2](#). Solicited injection site measurements will not be used to halt the study.

If any of the halting rules are met following any subject receipt of study vaccination, then this study will not continue with the remaining enrollments or study vaccinations without a review by and recommendation from the DSMB to proceed.

DMID retains the authority to suspend additional enrollment and study interventions/administration of study product during the entire study, as applicable.

